| | Screening | Baseline | Day 1 | Day 1 | Day 2 | | Day 3 | | Day 4 | | Day 5 | | Day 6 | |
| | Visit 1 | | Visit 1 | Visit 2 | Visit 3 | Visit 4 | Visit 5 | Visit 6 | Visit 7 | Visit 8 | Visit 9 | Visit 10 | Visit 11 | |
| | Hours Post First Dose ► | | 12 hrs | 24 hrs | 36 hrs | 48 hrs | 60 hrs | 72 hrs | 84 hrs | 96 hrs | 108 hrs | 120 hrs | | |
| Prior and Concomitant / Medication History and Diary Review ^a | X | | | X | X | X | X | X | X | X | X | X | X | |
| Vital signs (incl. temperature) ^b | X | | | | | | | | X | | | | X | |
| Physical examination (injury assessment) ^c | X | | | X | | X | | X | | X | | X | | |
| Urine pregnancy test | X ^f | | | | | | | | | | | X ^f | | |
| Randomization/Kit assignment | | X ^d | | | | | | | | | | | | |
| IMP administration ^e | | | X | X | X | X | X | X | X | X | X | X | | |
| Global Assessments | | | | | X ^g | | X ^g | | X ^g | | | | X ^g | |

^a Diary review begins at Visit 2^b Vital signs (blood pressure, respiratory rate, heart rate and body temperature after 5 minutes of rest in a sitting position).^c Full physical exam and injury assessment at Visit 1, limited exam (injury assessment) at all other visits^d Randomization to treatment occurs only for eligible patients.^e All topical IMP treatments must be weighed on a digital scale, then applied by the unblinded study staff at the site. Patient will wear a blindfold when being treated.^f Urine pregnancy test must be performed (for female patients) and the results must be negative (not pregnant) before dosing and at Visit 10^g Assessments by the patient will be completed before first rescue medication is taken. If between visits, then the investigator will complete assessments at the next scheduled visit.

Protocol Amendment Summary of Changes Table**Protocol Amendment 2 (Version 3.0)**

The following sections were amended from Version 2.0 to Version 3.0.

Type of Amendment: Substantial

Significant Changes:

Changes which are considered significant or substantial have been made to the following sections reflected below:

| Page Number | Section Number | Paragraph or Bullet point/number |
|-------------|----------------|--|
| 21 | 5.2 | 
Exclusion Criteria 15
 
15. Ice and compression are prohibited from the time of injury through the final evaluation. Application of standard care by rest, ice, compression (non-occlusive bandage) or elevation (RICE) may be considered at the discretion of the investigator
 |
| 41 | 9.1 | 
Statistical Hypotheses
 
The purpose of the study is to gather preliminary data for the efficacy and safety of the IMP. Therefore, there is no statistical hypotheses to be formulated.
 
For the comparison of the test gel vs. placebo, the primary efficacy hypothesis to be tested is the equality of Algometry AUC 0-72; the second is the POM VAS AUC 0-72.
 |
| 41 | 9.2 | 
Sample Size Determination
 
The study is not statistically powered. From feasibility point of view, sufficient number of participants will be randomized to study intervention in order to achieve an estimated total of 30 evaluable participants for each active treatment (naproxen gel or diclofenac gel) and 15 evaluable participants for placebo gel.
 
This is a proof of concept study and therefore a specific statistical power calculation cannot be applied, however, assuming a comparable effect of the test gel vs. diclofenac – as suggested by pharmacological studies-, reference is made to similar studies (Predel, Br J Sports Med 2004;38:318–323), in which the standardized effect sizes of Algometry AUC 0-72 and POM VAS AUC 0-72 were over 1; with 30:15
 |

| | | |
|----|-----|--|
| | | patients, a drop out rate of 10%, and a two-sided significance level $\alpha = 5\%$, a power $1 - \beta$ of about 80% is reached. |
| 44 | 9.3 | Analysis Sets – Per Protocol The primary efficacy analysis population will be PP population and ITT Population will be secondary. The same analysis on ITT Population will be repeated for the primary, and secondary and other efficacy endpoints to assess the robustness of the results based on PP Population. |
| 44 | 9.4 | Statistical Analysis This section is a summary of the planned statistical analyses of the most important endpoints including primary and secondary, and other-key endpoints. |

Additional Changes:**Not applicable**

Protocol Amendment Summary of Changes Table**Protocol Amendment 3 (Version 4.0)**

The following sections were amended from Version 3.0 to Version 4.0.

Type of Amendment: Substantial

Significant Changes:

Changes which are considered significant or substantial have been made to the following sections reflected below:

Sponsor Signatory – amended

PPD

PPD [REDACTED], Global Medical Affairs

Bayer Healthcare LLC.

PPD

PPD

Global Medical Category Pain

Medical and Clinical Affairs

Bayer Healthcare LLC.

Table of Contents

| | |
|--|-----------|
| Title Page..... | 1 |

1.1 Synopsis

Protocol Title: Randomized, Controlled, Double-blind, Placebo-controlled, Multi-center Hypothesis-finding Trial to Compare the Efficacy and Safety of a 10% Naproxen Gel vs. a 2.32% Diclofenac Diethylamine Gel and Placebo in the Treatment of Acute Soft Tissue Injuries of the Lower Extremities

Rationale: Proof of concept study to determine the effectiveness of naproxen gel 10% in participants with lower extremity injuries.

Objectives and Endpoints:

| Objectives | Endpoints |
|--|--|
| Primary 
To assess the effectiveness of a naproxen gel 10%, diclofenac diethylamine gel 2.32% and placebo for relieving tenderness to pressure in subjects with acute soft tissue injuries of the lower extremities. | 
Tenderness (Algometry) over the initial 72 hours (Algometry AUC 0-72). |
| Secondary 
To assess the safety of a naproxen gel 10%, diclofenac diethylamine gel 2.32% and placebo during a 5 day treatment period.To assess adverse events. | 
Safety (percentage of subjects with at least one TEAE);Incidence of adverse events. |

| Objectives | Endpoints |
|---|---|
| Other 
 • To evaluate pain on movement and tenderness to pressure over various time periods and at individual time points. | Endpoints 
 • VAS POM over the initial 12-hours (VAS AUC 0-12), 24-hours (VAS AUC 0-24), 36-hours (VAS AUC 0-36), 48-hours (VAS AUC 0-48), 60-hours (VAS AUC 0-60), 72-hours (VAS AUC 0-72), and 120 hours (VAS AUC 0-120); • Change of VAS POM at hours 12, 24, 36, 48, 60, 72 and 120 from baseline; • Change of Algometric Tenderness (N/cm²) at hours 12, 24, 36, 48, 60, 72 and 120 from baseline; • Algometric Tenderness (N/cm²) over the initial 12-hours (N/cm² AUC 0-12), 24-hours (N/cm² AUC 0-24), 36-hours (N/cm² AUC 0-36), 48-hours (N/cm² AUC 0-48) 60-hours (N/cm² AUC 0-60) and 120 hours (N/cm² AUC 0-120); • Ratio of algometry injured/contralateral sites over 72 hours and 120 hours (N/cm² Ratio AUC 0-72 and N/cm² Ratio AUC 0-120); • Percent of subjects with no (zero) VAS POM at 120 hours; • Global assessment of treatment efficacy at 24 hours, 48 hours, 72 hours and 120 hours by patients using a 5-point scale (0=none, 1=poor, 2=fair, 3=good, 4=excellent); • Global assessment of treatment efficacy at 24 hours, 48 hours, 72 hours and 120 hours by investigators using a 5-point scale (0=none, 1=poor, 2=fair, 3=good, 4=excellent). |

Overall Design: This is a randomized (2:2:1/naproxen:diclofenac:placebo), stratified by injury (contusion or sprain/strain) active- and placebo-controlled (vehicle), double-blind, multi-center (3 sites), parallel study.

Brief Summary:

This is a 6-day clinical trial to test the hypothesis that naproxen gel 10% safely and effectively relieves tenderness to pressure in subjects with acute soft tissue injuries of the lower extremities. Subjects who present to the study within 3 hours of injury will be recruited for the study. In order to assure adequate representation of different types of soft tissue injuries, subjects may enter the study with a lower extremity sprain/strain injury or a lower extremity contusion injury. Eligible subjects will be selected immediately following screening/baseline evaluations. Following selection, subjects will enter the Treatment Phase and will be randomly assigned to one of the three treatment groups- naproxen topical gel 10% (test); diclofenac diethylamine topical gel 2.32% (active comparator); or placebo gel. The randomization assignment is such that there is a

1 in 5 chance of receiving the placebo treatment. Treatment consists of a twice daily application (approximately 12 hours apart) of the assigned topical gel over 5 consecutive days, beginning on the evening of Day 1 and ending (last application) on the morning of Day 6 (total of 10 applications). All treatment applications will be performed by study staff at the site. After the first treatment, two visits each day for five consecutive days are required. Patients who experience a treatment failure can have the option of taking rescue medication for pain relief.

During the screening/baseline and follow-up treatment visits, tenderness will be measured by the pressure required to elicit a response. Pain on movement will also be rated by the subject using a 100 mm visual analogue scale.

Approximately 100 participants will be screened to achieve 75 randomized to study intervention for an estimated total of 30 evaluable participants per each active treatment and 15 participants in the placebo treatment.

Study Duration: 6 days

Treatment Duration: 6 days

Visit Frequency: After the first treatment, two visits each day for five consecutive days

Condition/Disease: Soft tissue injury, either a sprain/strain or contusion

Study Hypothesis: Topical naproxen gel, 10% effectively relieves tenderness to pressure in patients with acute soft tissue injuries

Health Measurement/Observation: Algometry measurements for tenderness and Visual Analog Scales for pain will occur pre and post topical treatment.

Number of Participants: Approximately 100 participants will be screened to achieve 75 randomized to study intervention for an estimated total of 30 evaluable participants per each active cohort and 15 participants in the placebo cohort.

Intervention Groups: Participants will be randomized in 2:2:1 fashion and stratified by injury type with at least 25 participants in the Sprain/Strain cohort and at least 50 participants in the Contusion cohort.

Data Monitoring/Other Committee: No

1.2 Scheme

1.3 Schedule of Activities (SoA) - amended

| Trial Procedure | Screening Phase | | Treatment Phase | | | | | | | | | |
|--|-------------------------|----------------|-----------------|---------|----------------|---------|----------------|---------|----------------|---------|----------------|----------------|
| | Screening | Baseline | Day 1 | | Day 2 | | Day 3 | | Day 4 | | Day 5 | |
| | Visit 1 | | Visit 1 | Visit 2 | Visit 3 | Visit 4 | Visit 5 | Visit 6 | Visit 7 | Visit 8 | Visit 9 | Visit 10 |
| | Hours Post First Dose ► | | 12 hrs | 24 hrs | 36 hrs | 48 hrs | 60 hrs | 72 hrs | 84 hrs | 96 hrs | 108 hrs | 120 hrs |
| Signed Informed Consent | X | | | | | | | | | | | |
| Inclusion/Exclusion Criteria Review | X | | | | | | | | | | | |
| Patient Demographics | X | | | | | | | | | | | |
| Medical History | X | | | | | | | | | | | |
| Prior and Concomitant / Medication History and Diary Review ^a | X | | | X | X | X | X | X | X | X | X | X |
| History of drug, alcohol and tobacco use | X | | | | | | | | | | | |
| Body weight, height, and BMI | X | | | | | | | | | | | |
| Vital signs (incl. temperature) ^b | X | | | | | | | X | | | | X |
| Physical examination (injury assessment) ^c | X | | | X | | X | | X | | X | | X |
| Injury Stratification (cohort) | X | | | | | | | | | | | |
| Urine pregnancy test | X ^f | | | | | | | | | | X ^f | |
| Diary distribution/training | X | | | | | | | | | | | |
| Randomization/Kit assignment | | X ^d | | | | | | | | | | |
| IMP administration ^e | | | X | X | X | X | X | X | X | X | X | X |
| Dispense rescue medication | | X | | | | | | | | | | |
| Rescue medicine accountability | | | X | X | X | X | X | X | X | X | X | X |
| Algometry | | X | X | X | X | X | X | X | X | | | X |
| POM VAS | | X | X | X | X | X | X | X | X | | | X |
| Global Assessments | | | | | X ^g | | X ^g | | X ^g | | | X ^g |
| Sensory Questions | | | | | | | | | | | | X |
| Diary and rescue medicine return | | | | | | | | | | | | X |
| End of Study (pt. discharged) | | | | | | | | | | | | X |
| Adverse events | | | X | X | X | X | X | X | X | X | X | X |

^a Diary review begins at Visit 2^b Vital signs (blood pressure, respiratory rate, heart rate and body temperature after 5 minutes of rest in a sitting position).^c Full physical exam and injury assessment at Visit 1, limited exam (injury assessment) at all other visits^d Randomization to treatment occurs only for eligible patients.^e All topical IMP treatments must be weighed on a digital scale, then applied by the unblinded study staff at the site. Patient will wear a blindfold when being treated.^f Urine pregnancy test must be performed (for female patients) and the results must be negative (not pregnant) before dosing.^g Assessments by the patient will be completed before first rescue medication is taken. If between visits, then the investigator will complete assessments at the next scheduled visit.

2. Introduction

CCI

The product is to be used for the temporary relief of minor aches & pains of muscles & joints. This proof-of-concept trial will assess the efficacy and safety of a newly developed 10% naproxen gel formulation compared to a commercially available topical nonsteroidal anti-inflammatory drug (NSAID) gel and placebo in the treatment of common sports related, acute traumatic injuries.

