2.3.1 Risk Assessment

| Potential Risk of Clinical Significance | Summary of Data/Rationale for Risk | Mitigation Strategy |
|---|--|--|
| Study Intervention | | |
| The risks associated with naproxen gel 10% are mostly cutaneous and nonserious in nature and include application site reactions such as erythema, pruritus, skin irritation, burning skin sensation, and contact dermatitis. Subjects with hypersensitivity to naproxen, or to any excipient in the test products should avoid exposure and should be excluded from this study. | Naproxen Topical Gel IB section 5.3.3.5 Adverse events | 
The exclusion criteria for the study and the medical oversight of its conduct for the detection and treatment (if necessary) of adverse events are adequate for subject safety and no special risk mitigation measures are necessary.
 
The following strategies (as numbered below) will be employed to mitigate adverse event risks:
 
5.2 Exclusion criteria6.6 Dose modification6.7 Stopping rules6.9 Treatment of overdose7.1 Discontinuation of study intervention7.2 Participant discontinuation/ Withdrawal from study8.3 Safety assessments8.4.3 Follow up of AEs and SAEs |
| Study Procedures | | |
| Subject may have an underlying medical condition uncovered during screening and baseline procedures. | | Investigator will advise subject to seek appropriate medical attention. |

| Other | | |
|--|--|--|

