8.1.12 Visit 11 (Day 6 evening, End of Study)

Patients will return to the site approximately 12 hours after Day 6 morning dosing. The following activities will be performed:

- Cleaning of the treated area by the unblinded staff
- Vital signs (blood pressure, heart rate, respiratory rate and body temperature after 5 minutes in a sitting position);
- Review diary for rescue/concomitant medications;
- Rescue medicine drug accountability;
- Adverse Event assessment;
- POM VAS;
- Algometry measurements;
- Global assessments for efficacy and tolerability;
- Sensory questions related to smell and touch;
- Return of diary and rescue medication.

No topical treatment is performed for this visit. Upon return of all study materials and completion of all study procedures, the patient will be discharged from the study.

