8.3.1 Physical Examinations

A general physical examination will include the injured extremity and assessments of the Dermatological, Cardiovascular, Respiratory, Gastrointestinal and Neurological systems at Screening (Visit 1). Height and weight will also be measured and recorded.

A limited physical examination of the injured extremity will be performed at Visits 2, 4, 6, 8 and 10. Changes related to the physical exam will be documented on the source documents and case report form.

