8.4 Adverse Events (AEs), Serious Adverse Events (SAEs) and Other Safety Reporting

The definitions of adverse events (AEs) and serious adverse events (SAEs) can be found in Section 10.3. The definition of unsolicited and solicited AEs can be found in Section 10.3.

AEs will be reported by the participant (or, when appropriate, by a caregiver, surrogate, or the participant's legally authorized representative).

The investigator and any qualified designees are responsible for detecting, documenting, and recording events that meet the definition of an AE or SAE and remain responsible for following up all AEs (see Section 7).

The method of recording, evaluating, and assessing causality of AEs and SAEs and the procedures for completing and transmitting SAE reports are provided in Section 10.3.

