8.4.3 Follow-up of AEs and SAEs

After the initial AE/SAE report, the investigator is required to proactively follow each participant at subsequent visits/contacts. All SAEs will be followed until resolution, stabilization, the event is otherwise explained, or the participant is lost to follow-up (as defined in Section 7.3). Further information on follow-up procedures is provided in Section 10.3.

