10.1.4 Informed Consent Process

The investigator or his/her representative will explain the nature of the study to the participant or his/her legally authorized representative and answer all questions regarding the study.

Participants must be informed that their participation is voluntary. Participants will be required to sign a statement of informed consent that meets the requirements of 21 CFR 50, local regulations, ICH guidelines, Health Insurance Portability and Accountability Act (HIPAA) requirements, where applicable, and the IRB/IEC or study center. Each participant will be informed about the following aspects of premature withdrawal:

- Each participant has the right to withdraw from the study at any time without any disadvantage and without having to provide reasons for this decision.
- The participant's consent covers examinations as specified in the visit description described in Section [8.1.12](#) to be conducted after withdrawal of consent.
- The participant's data that have been collected until the time of withdrawal will be retained and statistically analyzed in accordance with the statistical analysis plan.
- Participant-specific data on the basis of material obtained before withdrawal may be generated after withdrawal (e.g., image reading, analysis of biological specimen such as blood, urine or tissues); these data would also be retained and statistically analyzed in accordance with the statistical analysis plan. The participant has the right to object to the generation and processing of this post-withdrawal data. For this, he/she needs to sign a corresponding declaration of objection; alternatively, the participant's oral objection may be documented in the participant's source data.

Each participant will have ample time and opportunity to ask questions.

Only if the participant agrees to sign the informed consent form and has done so, may he/she enter the study. Additionally, the investigator will personally sign and date the form. The participant will receive a second original of the informed consent form.

The medical record must include a statement that written informed consent was obtained before the participant was enrolled in the study and the date the written consent was obtained. The authorized person obtaining the informed consent must also sign the ICF.

Participants must be consented to the most current version of the ICF(s) during their participation in the study.

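### No examination of the injured extremity is scheduled after the tenth application or defined for early discontinuation, and SoA footnote c, read literally, conflicts with the examination schedule

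*Protocol*

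**What the plan says.** - **Dosing.** The synopsis (protocol 1.1) has twice-daily applications "ending (last application) on the morning of Day 6 (total of 10 applications". Protocol 8.1.11 places the tenth at Visit 10.
- **Examination schedule.** SoA footnote c, which SAP 5.6 repeats, reads "Full physical exam and injury assessment at Visit 1, limited exam (injury assessment) at all other visits". Protocol 8.3.1 says "A limited physical examination of the injured extremity will be performed at Visits 2, 4, 6, 8 and 10". SAP 5.2 gives the same five visits, allows further examinations whenever the investigator thinks one is needed, and has any issue found at the limited examination recorded as an adverse event (AE).
- **Visit 11.** Protocol 8.1.12: "Patients will return to the site approximately 12 hours after Day 6 morning dosing". It lists cleaning, vital signs, diary review, rescue accountability, AE assessment, pain on movement, algometry, global ratings and sensory questions, followed by discharge. It lists no physical examination.
- **Risk.** Protocol 2.3.1: "The risks associated with naproxen gel 10% are mostly cutaneous and nonserious in nature". Sections 8.3 and 8.4.3 are among the mitigations it cites.
- **Early exit.** Protocol 7.2 asks for an early discontinuation visit where possible and refers to the SoA for its content. On withdrawal of consent, 10.1.4 says that the participant's "consent covers examinations as specified in the visit description described in Section" 8.1.12.
- **AE follow-up.** Under 8.4 the investigator and designees "remain responsible for following up all AEs (see Section 7". Under 8.4.3, "All SAEs will be followed until resolution, stabilization, the event is otherwise explained".

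**The concern.** Safety is the secondary objective, and its endpoint is the percentage of participants with at least one treatment-emergent AE (TEAE). The limited examination feeds that endpoint directly, because what it finds becomes an AE. For a gel whose stated risks are mainly cutaneous, one would expect the treated limb to be looked at once after the full course. Vital signs are scheduled at Visit 11, so an end-of-treatment safety check was intended, but it leaves out the site of the main named risk.

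Two wording problems add to this. A site that follows footnote c literally and a site that follows 8.3.1 would collect different safety data in a three-site trial. A site handling an early discontinuation has no list of procedures to work from.

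**Working it through.** The plan states no figure to reproduce. The check is a count of examinations against applications. Visit times are from SAP section 3, applications from protocol 8.1.2 to 8.1.12, and examinations from 8.3.1, the visit lists and SAP 5.2. At Visits 2 to 10 the assessments are listed before that visit's application, so the number of applications already received at Visit k is k − 1.

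| Visit | Hours | Applications received at assessment | Limited exam scheduled | Footnote c, literal |
|---|---|---|---|---|
| 2 | 12 | 1 | yes | yes |
| 3 | 24 | 2 | no | yes |
| 4 | 36 | 3 | yes | yes |
| 5 | 48 | 4 | no | yes |
| 6 | 60 | 5 | yes | yes |
| 7 | 72 | 6 | no | yes |
| 8 | 84 | 7 | yes | yes |
| 9 | 96 | 8 | no | yes |
| 10 | 108 | 9 | yes | yes |
| 11 | 120 | 10 | no | yes |

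1. Scheduled post-baseline examinations: 5 of 10 visits. Footnote c read literally: 10 of 10. The difference is Visits 3, 5, 7, 9 and 11.
2. Visits 3, 5, 7 and 9 are each followed by an examination 12 h later. Visit 11 is not, so it is the only one of the five that leaves a lasting gap.
3. Exposure at the last examination: 9/10 = 90% of applications. Time left uncovered: 120 − 108 = 12 h. Scheduled examinations after application 10: 0.

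**Early discontinuation.** Section 7.2 sends the reader to the SoA, and the SoA has no early-discontinuation column. The content of that visit, including any examination, is therefore undefined. Section 10.1.4 covers withdrawal of consent and leads to 8.1.12, which has no examination.

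**AE follow-up.** Section 8.4 covers all AEs but points to Section 7. Sections 7.1 to 7.3 deal with stopping treatment, withdrawal and loss of contact, and contain no AE follow-up rule. Section 8.4.3 requires follow-up of AEs and SAEs at later visits or contacts, but states an end point for SAEs only. Section 10.3.3 obliges the investigator to arrange further evaluations of an AE or SAE where medically indicated. Section 4.1.1.3 has no follow-up phase. How these apply to a non-serious AE still open at Visit 11 is not stated.

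**The case against.** The strongest reply is that Visit 11 is not a blank. The area is cleaned, algometry is done at the marked site by staff not involved in dosing, AEs are assessed, the diary is reviewed, and both patient and investigator rate tolerability. SAP 5.2 lets the investigator examine at any time and does not make this depend on a complaint. Protocol 10.3.1 also defines solicited AEs, including local events at the application site about which the participant is specifically asked. In a 6-day proof-of-concept trial with purely descriptive safety analysis, the Visit 10 examination already covers 9 of 10 applications.

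Most of this stands, and it rules out several stronger readings:

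- A reader might infer that the site is never looked at after full exposure. The documents support only that no physical examination is scheduled then.
- A reader might infer that footnote c promises ten examinations. It is attached to the examination row and can equally be read as giving the type of examination at the marked visits.
- A reader might infer that participants who withdraw because of a skin reaction drop out of the TEAE percentage. They do not, since the reaction that led to withdrawal is already an AE. Those who only stop the gel stay in the study under 7.1 and keep their remaining examinations.
- A reader might infer from 10.1.4 that the examination is excluded at early exit. The operative text is 7.2, and it leaves the content open.
- A reader might infer that non-serious AEs are not followed at all. Sections 8.4.3 and 10.3.3 contain duties that apply to them. Only the explicit end point is limited to SAEs.

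The reply does not fully close the gap. Unblinded staff do the cleaning, and 6.4 gives them no responsibility for AEs. Algometry yields a pressure value, and the tolerability item asks in general how the participant is doing. Section 8.3.1 has no counterpart to the SAP's clause on unscheduled examinations, and the protocol does not list the predefined local events. None of these is a scheduled, recorded look at the treated skin.

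**Conclusion.** The point holds as a minor one. No examination of the injured extremity is scheduled after the tenth application, none is specified for early discontinuation, and footnote c conflicts with the rest of the schedule if read literally.

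Among participants who complete the trial, the practical gap is confined to reactions that first appear in the last 12 h and are missed by every other Visit 11 assessment. Its effect on the TEAE percentage cannot be derived, because the documents give neither an incidence of local reactions nor a detection rate for the other assessments. It is probably small. The conclusion rests on the order in which 8.1.11 lists the Visit 10 examination and the tenth application, and on the five visits named alike in 8.3.1 and SAP 5.2. The AE follow-up wording is a separate inconsistency and does not affect this conclusion.

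**What to change.** 1. Add the existing limited examination of the injured extremity, stated to include the application site, to Visit 11 in the SoA row, protocol 8.1.12 and 8.3.1, and SAP 5.2 with its copy of the schedule in 5.6. The application site needs naming because 8.3.1 mentions a dermatological assessment only at Visit 1.
2. Add an early-discontinuation column to the SoA that includes this examination, so that the reference in 7.2 has a target.
3. Reword footnote c so that it agrees with the row.
4. Separately, reconcile 8.4 with 8.4.3 and 10.3.3 and correct the pointer to Section 7. The content of the follow-up rule is for the sponsor to decide.

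The cost is a few minutes at a visit the participant already attends, on a limb already cleaned and handled for algometry, plus text edits. The planned analysis does not change: SAP 14.5 already lists abnormal examination findings and summarises TEAEs.
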